APPENDIX 2 ADVERSE EVENTS OF SPECIAL INTEREST

FDA Requested AESI Terms	MedDRA Preferred Term Search Criteria for Defining AESI
Any event of seizure, seizure-like phenomena	Seizure Seizure like phenomena Generalised tonic-clonic seizure Seizure cluster Simple partial seizures Focal dyscognitive seizures Seizure anoxic Petit mal epilepsy Atonic seizure Clonic convulsion Febrile convulsion Tonic convulsion Autonomic seizure Partial seizures Generalised onset non-motor seizure Partial seizures with secondary generalisation
Loss of consciousness and altered state of consciousness	Loss of consciousness Depressed level of consciousness Consciousness fluctuating Slow response to stimuli Hyporesponsive to stimuli Unresponsive to stimuli Stupor Syncope
Tardive dyskinesia	Tardive dyskinesia
Acute dystonic reactions	Dystonia Oromandibular dystonia Torticollis Blepharospasm Pharyngeal dystonia Writer's cramp Early onset primary dystonia Oculogyric crisis Opisthotonus Trismus Tic Emprosthotonus
Akathisia	Akathisia
Acute Parkinsonian symptoms	Parkinsonism Parkinsonian gait Tremor Parkinsonian rest tremor Bradykinesia

FDA Requested AESI Terms	MedDRA Preferred Term Search Criteria for Defining AESI
	Cogwheel rigidity Reduced facial expression

APPENDIX 3 CLINICAL LABORATORY EVALUATIONS

The tests detailed in [Table 3](#) will be performed by a central laboratory.

Protocol-specific requirements for inclusion or exclusion of participants are detailed in Section 5 of the protocol.

Additional tests may be performed at any time during the clinical trial as determined necessary by the Investigator or required by local regulations.

Table 3 Protocol-Required Laboratory Assessments

Clinical Chemistry	Hematology	Urinalysis
Alanine aminotransferase (ALT)	Hematocrit	Bilirubin
Alkaline phosphatase	Hemoglobin	Glucose
Aspartate aminotransferase (AST)	Mean corpuscular hemoglobin	Ketones
Blood urea nitrogen (BUN)	Mean corpuscular hemoglobin concentration	Leukocyte esterase
Calcium	Mean corpuscular volume	Nitrite
Creatinine	Platelet count	Blood
Glucose	Red blood cell (RBC) count	pH
Potassium	RBC distribution width	Specific gravity
Sodium	White blood cell (WBC) count	Protein
Total and direct bilirubin	WBC differential (absolute):	Urobilinogen
Total protein	
 • Basophils • Eosinophils • Lymphocytes • Monocytes • Neutrophils 	Microscopic exam including bacteria, casts, crystals, epithelial cells, RBCs, and WBCs (if protein, leukocyte esterase, nitrite, or blood is positive)

Drug Screen	Coagulation Factors (Screening only)	Other Tests
Including but not limited to: Amphetamines Barbiturates Benzodiazepines (Stable use of ≤ 2 mg of lorazepam/day is allowed) Cannabinoids (THC) Cocaine (metabolite) Methadone Opiates Phencyclidine	Activated partial thromboplastin time Prothrombin time and international normalized ratio	Serum and urine pregnancy, (women of childbearing potential only) Viral Serology Screen (at Screening only): Hepatitis B surface antigen (HBsAg) and Hepatitis C (HCV) antibody and HIV antibody/antigen Urinary albumin Urinary creatinine (Part A only)

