- E 13. The participant has any of the following at the Screening visit: a serum total bilirubin value $>1.5 \times \text{ULN}$; a serum alanine aminotransferase (ALT) or aspartate aminotransferase (AST) value $>2 \times \text{ULN}$. As an exception, participants that present with elevated bilirubin in the absence of elevations in ALT or AST that fits the pattern of Gilbert's syndrome may be enrolled after discussion with the medical monitor if their conjugated bilirubin is within the ULN.
- E 14. Criterion removed from protocol in Version 5.0.
- E 15. History of any suicide attempt within the past 2 years.
- E 16. History of structural heart disease (eg, congestive heart failure, depressed ejection fraction or left ventricular hypertrophy) or clinically significant cardiac arrhythmias (eg ventricular tachycardia) excluding sinus arrhythmia.
- E 17. History of cancer treated with chemotherapy
- E 18. Any other significant disease, disorder, lab abnormalities, or environmental factor that, in the opinion of the Investigator or Sponsor, may either put the participant at risk due to participation in the clinical trial, may influence or confound the result of the clinical trial, or affect the participant's ability to participate in the clinical trial.
- E 19. Has previously received treatment with PRAX-944 in any clinical trial (including Part A of the current trial for participants enrolling in Part B)

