4.10.2 Laboratory Test Results

Blood and urine samples will be collected by site staff for clinical laboratory testing. Urine pregnancy tests will be performed at the site and will be recorded in the eCRF as “Positive” or “Negative”. All other samples will be analyzed at the central laboratory. For all samples collected, the following data will be recorded in the eCRF: test category (ie, Chemistry, Hematology, Urinalysis, Coagulation, Pregnancy Test, Viral Serology or Urine Drug Screen), sample collection date, and sample time. For urine pregnancy tests, the result will also be recorded in the eCRF as “Positive” or “Negative”. An indicator for whether a repeat sample was taken (Yes/No) will also be recorded in the eCRF for each sample collected.

Collected laboratory samples will then be processed at the central laboratory for the calculation of reported values for the laboratory tests listed in [Appendix 3](#). Central laboratory data will include test category, lab test name, reported result, reported unit, reported reference range (ie, low and high), and abnormal indicator. Data from the central laboratory will be combined with the laboratory eCRF data prior to analysis.

Change from baseline values to each post-baseline assessment will be calculated for all continuous laboratory tests.

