5.8.2 Laboratory Test Results

Descriptive statistics for all reported and change from baseline values will be summarized by test category, laboratory test, and visit. Only the original assessment for each visit day will contribute to descriptive statistics; repeat or unscheduled assessments will not be included in the calculation of descriptive statistics by visit. All laboratory test results data (including pregnancy test and urine drug screen data and any repeat or unscheduled assessments) will be listed by study part, participant, and visit.

Descriptive statistics for all reported and change from baseline values for KIM-1, urine creatinine, and KIM-1 per urine creatinine ratio will be summarized by test and visit. Results will be listed by study part, participant, and visit.

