5.8.3 Vital Sign Results

Descriptive statistics for all reported and change from baseline values will be summarized by visit. Only the original assessment for each timepoint will contribute to these summaries; repeat or unscheduled assessments will not be included in the calculation of descriptive statistics by timepoint. The number and percentage of participants with PCI values at any time will be tabulated by treatment group. Summaries of PCI values will include all assessments regardless of whether an original, repeat, or unscheduled assessment. All vital sign results data will be listed by study part, participant, and visit.

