5.8.4 ECG Results

Descriptive statistics for all reported and change from baseline values will be summarized by visit. Only the original assessment for each visit will contribute to these summaries; repeat or unscheduled assessments will not be included in the calculation of descriptive statistics. The number and percentage of participants with PCI values at any time will be tabulated by treatment group; the number and percentage of participants with abnormal ECG findings will be presented similarly. Summaries of PCI values and abnormal ECG findings will include all assessments regardless of whether an original, repeat, or unscheduled assessment. All ECG results data will be listed by study part, participant, and visit.

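### The Part B laboratory tables give no count of participants with out-of-range results, and repeat or unscheduled post-dose results reach listings only

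*SAP*

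**What the plan says.** The operative text is SAP 5.8.2. It plans one kind of summary: "Descriptive statistics for all reported and change from baseline values will be summarized by test category, laboratory test, and visit". On which results count, it says "Only the original assessment for each visit day will contribute to descriptive statistics", and adds that "repeat or unscheduled assessments will not be included in the calculation of descriptive statistics by visit". Repeat and unscheduled results are listed by participant. The only other laboratory summary in that section is the same kind of description for KIM-1 and urine creatinine.

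SAP Appendix 3, like Protocol Appendix 1, shows that tests outside the schedule are foreseen: "Additional tests may be performed at any time during the clinical trial as determined necessary by the Investigator or required by local regulations". SAP 4.10.2 says that the central laboratory file carries "reported reference range (ie, low and high), and abnormal indicator". Section 5.8.2 specifies no summary that uses either item.

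For vital signs, SAP 5.8.3 also keeps repeat and unscheduled values out of the by-timepoint statistics. It then tabulates the number and percentage of participants with potentially clinically important (PCI) values at any time: "Summaries of PCI values will include all assessments regardless of whether an original, repeat, or unscheduled assessment". SAP 5.8.4 does the same for ECG: "Summaries of PCI values and abnormal ECG findings will include all assessments regardless of whether an original, repeat, or unscheduled assessment". The criteria are in SAP 4.10.3 (Table 1) and 4.10.4 (Table 2).

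Protocol 3.2 and SAP 2.1 list laboratory change among the five Part B primary safety endpoints.

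**The concern.** A safety reader first asks how many participants had an abnormal value and how far it moved from where they started. By-visit mean, SD, median, minimum and maximum do not answer that. They do not give the number outside the reference range, and they do not show whether extremes at two visits belong to the same person.

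The SAP recognises this for vital signs and ECG, where it sets the exclusion of extra assessments against an any-time participant count. For laboratory tests it keeps the exclusion and omits the count. A result obtained between visits then has no place in any laboratory table. It reaches an adverse event table only if the investigator judges it clinically significant. What is at stake is how completely the Part B tables report a primary safety endpoint in a trial meant to inform later controlled studies.

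**Working it through.** **Plan's own figure.** The only safety figure in the sample size text (Protocol 9.1, SAP 2.3) is an 80% probability of seeing at least one adverse event of 15% incidence in 10 participants. It reproduces: 1 − 0.85^10 = 0.803. It concerns adverse events and is not used below.

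**The five Part B primary safety endpoints side by side**

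| Endpoint | Count of participants affected planned? | Extra assessments in that count? |
|---|---|---|
| Adverse events (SAP 5.8.1) | Yes | Not applicable |
| Vital signs (SAP 5.8.3) | Yes, PCI at any time | Yes |
| ECG (SAP 5.8.4) | Yes, PCI and abnormal findings | Yes |
| C-SSRS (SAP 5.8.5) | Yes | Not applicable |
| Laboratory tests (SAP 5.8.2) | No | Extra results listed only |

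Laboratory change is the only one of the five without a participant count.

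**Scheduled sampling against the planned titration.** Inputs are the dose calendar in footnote k of the Part B schedule and the laboratory row of that schedule (Protocol Table 3, SAP Appendix 1). The laboratory entries for Days 56 and 70 cannot be read in the supplied text and are not used.

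| Planned dose | Days | Number of days | Visible scheduled post-dose lab |
|---|---|---|---|
| 20 mg | 1–3 | 3 | none |
| 40 mg | 4–7 | 4 | Day 7 |
| 60 mg | 8–14 | 7 | none |
| 80 mg | 15–21 | 7 | Day 21 |
| 100 mg | 22–28 | 7 | none |
| 120 mg | 29–42 | 14 | Day 42 |

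For a participant who follows every planned step, the levels without a scheduled post-dose lab cover 3 + 7 + 7 = 17 of 42 days.

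**How often only an unscheduled test could show a transient abnormality.** Assumptions: onset equally likely on each of Days 1–42, a fixed duration of L days, and visits on their nominal days. An onset on day o is seen at a scheduled lab on day s (7, 21 or 42) if o ≤ s ≤ o + L − 1.

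- L = 3: 3 + 3 + 3 = 9 onset days are seen, so 33/42 = 79% are missed.
- L = 7: 7 + 7 + 7 = 21 are seen, so 21/42 = 50% are missed.
- L = 14: 7 + 14 + 14 = 35 are seen, so 7/42 = 17% are missed.

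This depends on visit days, not dose, so dose reductions do not change it. It shows where an unscheduled test would be the only source. It does not say how often abnormalities occur or how often such tests are drawn.

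**The case against.** The strongest reply is that most of what matters is caught elsewhere. Protocol 8.2.4 has the investigator review every laboratory report and record clinically significant adverse changes as adverse events, which are also a Part B primary endpoint. Every result is listed, and with about 12 to 24 participants the listings can be read in full. Protocol 9.3.2 promises only values and changes for laboratory tests, and the SAP delivers them. Table templates are held separately (SAP 5) and were not available.

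Much of this stands, and it narrows the point to tables. It does not remove it. Abnormal vital signs and ECGs can also become adverse events (Protocol Appendix 2), and Protocol 9.3.2 promises no more for them than for laboratory tests, yet the SAP added counts for both.

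Four stronger readings are tempting, and the documents do not support them:

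- *Results at 20, 60 or 100 mg can only come from unscheduled tests.* Protocol 4.1.2.2.1 and 6.6 let a participant return to a lower dose and continue on the same visit schedule. Someone returned from 120 to 100 mg has the Day 42 lab at 100 mg. Someone returned from 80 to 60 mg before Day 21 has the Day 21 and Day 42 labs at 60 mg.
- *The 15% incidence gives the expected number with abnormal labs.* That figure is for adverse events. No laboratory incidence is stated.
- *Abnormalities at scheduled visits are hidden.* An extreme value from the first sample of a visit prints as the minimum or maximum (SAP 5). It is visible but not counted. When an abnormal scheduled result is repeated, only the repeat is dropped.
- *Unscheduled results enter no laboratory statistic at all.* Under SAP 4, an unscheduled pre-dose value can serve as baseline.

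Appendix 3 is also not itself at fault. Its additional tests could include analytes outside Table 3, and treating them as the unscheduled assessments of 5.8.2 is an inference.

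**Conclusion.** The point holds as a gap in the laboratory tables. As written, SAP 5.8.2 does not give the number of participants with an out-of-range value, even for scheduled samples. Repeat and unscheduled post-dose results appear in listings only. The results that escape every table are first abnormalities found at an unscheduled test and not judged clinically significant.

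No number of participants can be attached to this from the documents. The 79%, 50% and 17% above are illustrations under stated assumptions about onset and duration. The conclusion rests on the text of the SAP, without sight of the table templates, and uses no Day 56 or Day 70 laboratory entries. It is a worthwhile correction to the reporting of a primary endpoint. It does not show that safety data are lost.

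**What to change.** In SAP 5.8.2, keep the by-visit statistics unchanged and add:

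1. For each chemistry and hematology test in Table 3 of Appendix 3, a shift table from baseline category (low, normal, high) to worst post-dose category, by part, phase and arm. Use all post-dose results, whether first, repeat or unscheduled. Where a test can be abnormal in both directions, show lowest and highest separately. State which baseline applies in the withdrawal phase, because SAP 4 defines the randomization baseline for efficacy endpoints only.
2. The number and percentage of participants with any post-dose ALT or AST above 2 × ULN, or total bilirubin above 1.5 × ULN. These are the Screening limits of exclusion criterion E 13, used here only as a reporting threshold. Apart from the Gilbert's syndrome exception, a value above them is new since Screening.
3. The number of post-dose tests per participant, beside the counts.

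The cost is SAP wording and one more standard table, with its count, from data already collected. The downside is that participants tested more often have more chances to show an abnormal value, which is why item 3 is needed.
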